# 5.7 Image/signal-guidance for target localization

- 5.7.1 After patient is setup on the treatment table, either the Calypso system or ExacTrac or cone-beam CT system will be used to align the patient with the treatment machine geometry based on the treatment plan. The alignment result will be evaluated by the attending physician and attending physicist and be approved for treatment by attending physician. The alignment data will be recorded.
- 5.7.2 If the Calypso tracking system is used for localization of the prostate, it will be used during the treatment to track the target motion. A correction action will be performed if the target migrated more than 2 mm for more than 20 seconds in any of three orthogonal coordinates.
- 5.7.3 If an ExacTrac system is used for prostate localization with implanted markers, stereotactic images should be taken at least twice during the treatment (or at least every 1 minute).
- 5.7.4 Cone-beam CT (CBCT) images should be taken prior to radiation delivery but after image-guidance with method described either with 6.7.2 or 6.7.3 and also taken immediately after the radiation treatment. For some special cases, CBCT images may be taken more frequently during the treatment per physician's clinical judgment.

- 5.7.5 The initial localizations and alignment is based on the center of mass of the transponders/fiducial markers. Significant rotations may be corrected at initial localization stage, and intra-fractional rotations will be ignored. Further adjustment during the treatment will be translational shift of the center of mass determined via Calypso or ExactTrac or CBCT, using remote couch motion.
- 5.7.6 The physicist will be on-site for image guidance and treatment. For any imageguidance procedure, comparison with reference images or baseline data should be performed and reviewed and approved by both physician and physicist on site. The comparison can be done both manually and automatically. For any imageguidance method, if any deviation is larger than 2 mm, correction should be performed.
- 5.7.7 All image/signal-guidance data should be recorded for post treatment review and analysis. In some case, replanning (either offline or online) based anatomy of the day may be performed. Such request will be made by the attending physician.

# 5.8 Radiation Toxicity

Patients will be seen weekly by their radiation oncologist during radiation therapy. Any observations regarding radiation reactions will be recorded and should include attention toward the following potential side effects:

- 5.8.1 Small bowel or rectal irritation manifesting as abdominal cramping, diarrhea, rectal urgency, proctitis, or hematochezia
- 5.8.2 Bladder complications including urinary frequency/urgency, dysuria, hematuria, urinary tract infection, and incontinence
- 5.8.3 Radiation dermatitis
- 5.8.4 Clinical discretion may be exercised to treat side effects from radiation therapy. Rectal side effects such as diarrhea may be treated with diphenoxylate or loperamide. Bladder or rectal spasms can be treated with anticholinergic agents or tolterodine. Bladder irritation can be managed with phenazopyridine. Dysuria may be managed with ibuprofen. Erectile dysfunction can be treated with phosphodiesterase (PDE) inhibitors (sildenafil).

## 5.9 Radiation Adverse Event Reporting

Adverse events (AEs) and serious adverse events (SAEs) will be recorded in study database. Related and unexpected SAEs will be reported to the DUHS IRB per IRB policy. Sites are responsible for reporting any related and unexpected SAEs to their respective IRBs and also for notifying [name] and his Study Coordinator of such an event in order to facilitate reporting to the DUHS IRB in accordance with the required reporting timelines. Conversely, the DUHS study team is responsible for notifying all study sites of any reportable events in a timely fashion.

Adverse Event Definition

Definition of an AE: Any unfavorable and unintended sign (including an abnormal laboratory finding), symptom, or disease temporally associated with the use of a medical treatment or procedure regardless of whether it is considered related to the medical treatment or procedure (attribution of unrelated, unlikely, possible, probable, or definite).

Definition of an SAE: Any adverse experience occurring at any dose that results in any of the following outcomes:

- Death;
- A life-threatening adverse experience;
- Inpatient hospitalization or prolongation of existing hospitalization;
- A persistent or significant disability/incapacity;
- A congenital anomaly/birth defect.

Important medical events that do not result in death, are not life threatening, or do not require hospitalization may be considered an SAE experience, when, based upon medical judgment, they may jeopardize the patient and may require medical or surgical intervention to prevent one of the outcomes listed in the definition.

# Note: All deaths on study require both routine and expedited reporting regardless of causality. Attribution to treatment or other cause must be provided. "On study" is defined as during or within 30 days of completing protocol treatment.

Expected events - Expected events are those that have been previously identified as resulting from treatment of prostate cancer with radiation therapy. For purposes of this study, reporting requirements are determined by the assessment of the following adverse event characteristics: the type or nature of the event; the severity (grade); the relationship to the study therapy and whether the event is expected or unexpected.

Recommended assessment steps include:

Identification of adverse events using the NCI CTCAE Version 4.0 terminology. A copy of the CTCAE can be downloaded from the CTEP home page (http://ctep.cancer.gov). Grading the severity of the adverse event using the NCI CTCAE Version 4.0. Determination as to whether the adverse event is related to the study therapy using the following categories: Unrelated, Possible, Probable, and Definite. Determine whether the adverse event is expected or unexpected.

#### **REPORTING REQUIREMENTS FOR SERIOUS ADVERSE EVENTS THAT OCCUR WITHIN 30 DAYS OF THE DATE OF THE LAST RADIATION TREATMENT**

	Grade 3 or 4	Grade 4	Grade 4 & 5
			Unexpected
	With	Without	
	Hospitalization	Hospitalization	
	-	Expected	
Unrelated, Unlikely	Not required	Not required	10 Calendar Days
Possible, Probable or	Unexpected	Not required	5 Calendar Days

Definite	10 Calendar Days	

Any late death (> 30 days after end of radiation) attributed to the protocol treatment should be reported within 10 calendar days of the PI learning of the event.

## **REPORTING REQUIREMENTS FOR SERIOUS ADVERSE EVENTS THAT** OCCUR > 30 DAYS OF THE DATE OF THE LAST RADIATION TREATMENT

	Grade 3 Unexpected with Hospitalization	Grade 4 & 5 Unexpected	Grade 4 & 5 Expected
Possible, Probable or	15 Calendar Days	10 Calendar Days	15 Calendar Days
Definite			-

# 6.0 Study Visits

## 6.1 Study Presentation

Following the request of the patient's radiation oncologist, the patient will be given the consent form, provided time to review it and ask any questions regarding his participation in the study. After the subject has consented, the study team will collect the information required to complete eligibility. The patient will be asked to complete the AUASS, IIEF and EPIC-26 if not already available from his previous clinical visit(s).

# 6.2 Treatment Planning

During this period, the subject will have prostate imaging and treatment planning per standard practice.

# 6.3 SBRT

During SBRT visits, the subject should receive therapy according to the treatment plan based on the anatomy of the day from the CBCT accomplished prior to each treatment. At each fraction, the physicist or designee should record the following information:

- The date and number of the fraction
- $\circ$  Whether the patient was successfully localized and tracked using the image guidance system.

• Whether the patient required any interventions due to the information provided by the image guidance system, if so the nature of the intervention

• If reoptimization is requested by the attending physician, the physicist will perform plan reoptimization based on the anatomy of the day and previous optimization results. The minimum QA for modified plan will include MU verification using an independent software and analysis of MLC delivery information in the Dialog file from the treatment machine.

## 6.4 Treatment Checks

Patients will be seen and evaluated weekly during radiation with documentation of tolerance, including acute reactions.

# 6.5 Follow-up Visits

Patients will be seen approximately at 1, 3, 6, 12, 18, 24, 36 months following the end of radiotherapy. Follow-up visits may occur at the Department of Radiation Oncology or with referring providers. At each visit (see table) the patient will have an interval history, focused physical examination (digital rectal examination at the physician discretion), and assessment of specific GU and GI toxicity. PSA will be assessed before or at each follow-up visit.

## 6.6 Patient Assessments

Patient assessments are described below, some variation with respect to visit timing is permissible to allow for individual patient needs and clinic schedules.

	Baseline	SBRT Planning	During RT	1 Mo	3 Mo	6 Mo	12 Mo	18 Mo	24 Mo	36 Mo
Medical History	Х									
Physical Exam	X (including DRE)			$\mathbf{X}^1$						
Planning CT/MR		Х	$X^2$							
Prostate Measurement	Х									
Transponder or Fiducial Marker Placement		Х								
AUASS, IIEF	Х			Х	Х	Х	Х	Х	Х	Х
EPIC-26 QOL	Х				Х		Х		Х	Х
Toxicity Assessment			X	X	X	X	X	X	X	X
PSA	$X^4$				Х	Χ	Х	Χ	Χ	Х

Focused physical exam. Digital rectal exam (DRE) at the discretion of the physician.

 CBCT to be performed prior to each treatment and reoptimization performed if needed.

 As per standard clinic practice.

 Baseline PSA must be within 180 days of study registration.

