# **3.3** Exclusion Criteria

3.3.1 Prior or concurrent invasive malignancy (except non-melanomatous skin cancer) or lymphomatous/hematogenous malignancy unless continually disease free for a

minimum of 5 years. (For example, carcinoma in situ of the bladder or oral cavity is permissible)

- 3.3.2 Evidence of distant metastases (based on disease stage and clinical presentation)
- 3.3.3 Evidence of regional lymph node involvement (based on disease stage and clinical presentation)
- 3.3.4 Significant urinary obstruction (i.e. AUA Symptom score > 18)
- 3.3.5 Estimated prostate gland > 100 grams (within 8 weeks prior to study enrollment)
- 3.3.6 Previous radical surgery (prostatectomy) or cryosurgery for prostate cancer
- 3.3.7 Previous pelvic irradiation, prostate brachytherapy, or bilateral orchiectomy
- 3.3.8 Previous hormonal therapy, such as LHRH agonists (e.g. goserelin, leuprolide), anti-androgens (e.g., flutamide, bicalutamide), estrogens (e.g., DES), or surgical castration (bilateral orchiectomy) or planned concurrent androgen deprivation therapy
- 3.3.9 Previous or concurrent cytotoxic chemotherapy for prostate cancer
- 3.3.10 Prosthetic implants in the pelvic region that contain metal or conductive materials (e.g., an artificial hip).
- 3.3.11 Severe, active comorbidity, defined as follows:
  - Unstable angina and/or congestive heart failure requiring hospitalization within the last 6 months
  - Transmural myocardial infarction within the last 6 months
  - Acute bacterial or fungal infection requiring intravenous antibiotics at the time of registration
  - Crohn's Disease or ulcerative colitis
  - Chronic obstructive pulmonary disease exacerbation or other respiratory illness requiring hospitalization or precluding study therapy at the time of registration
  - Hepatic insufficiency resulting in clinical jaundice and/or coagulation defects; note, however, that laboratory tests for liver function and coagulation parameters are not required for entry into this protocol. (Patients on Coumadin or other blood thinning agents are eligible for this study.)
  - Acquired immune deficiency syndrome (AIDS) based upon current CDC definition; note, however, that HIV testing is not required for entry into this protocol. The need to exclude patients with AIDS from this protocol is necessary because the treatments involved in this protocol may be significantly immunosuppressive. Protocol-specific requirements may also exclude immunocompromised patients.

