## 4.1 Symptom Assessment and QOL Evaluation

(These may be performed prior to consent as they are routine for urology or radiation oncology clinics);

4.1.1 International Prostate Symptom Score (IPSS)/American Urological Association Symptom Score, International Index of Erectile Function (IIEF-5) and EPIC-26 QOL.

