## 5.2 Supportive Measures

5.2.1 Urinary

Symptomatic urinary medicines, (e.g. tamsulosin) are allowed at the discretion of the treating radiation oncologist or urologist.

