#### 6.8 Adverse Events Classification

Adverse events will be recorded at each study visit. These adverse events will be classified in accordance to the CTCAE ver. 4.0.

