# 9.3 Appendix 3 Data Collection: Dosimetry and Initial Evaluation

Patient	Initials: Subject Study	/ ID Number:	-
1.Prosta	ate volume (CTV)		сс
2.Prosta	ate planning target volume (PTV)		cc
3.Confo	ormality index (Volume of prescription isodose s	urface / volume of PTV)	
4. Minir	num dose to 1% of prostate planning target volu	me $(P + 0.3)$ .	Gy
5. Maxin	mum dose to 1% of prostate planning target volu	me(P+0.3) .	Gy
6.Mean	dose to the prostate planning target volume (P +	0.3)	Gy
7.Bladd	ler volume at time of planning CT		cc
8.Maxin	mal dose delivered to 2 cc or more of bladder		Gy
9.Perce	nt and absolute volume of bladder > 37 Gy (V10	0) %	cc
10.	Percent and absolute volume of bladder > 33 (	Gy (V90) %	cc
11.	Percent and absolute volume of bladder > 28	Gy (V75) %	cc
12.	Percent and absolute volume of bladder >24 C	iy (V65) %	сс
13.	Percent and absolute volume of bladder >18.5	Gy (V50) %	сс
14.	Mean dose to prostatic urethra		Gy
15.	Maximal dose to 10% of prostatic urethra	·	Gy
16.	Rectal volume at time of planning CT		cc
17.	Maximal dose delivered to 2 cc or more of rec		Gy
18.	Percent and absolute volume of rectum > 37 C	iy (V100)%	cc
19.	Percent and absolute volume of rectum $> 33$ C	у (V90)%	cc
20.	Percent and absolute volume of rectum $> 28$ C	ry (V75) %	cc
21.	Percent and absolute volume of rectum > 24 C	iy (V65) %	cc
22.	Percent and absolute volume of rectum > 18.5	Gy (V50) %	cc
23.	Mean dose to right femoral head	·	_ Gy
24.	Mean dose to left femoral head		_ Gy
25.	Energy	MV	Ţ
26.	Number of fields:		
27.	Non-axial beams?	Yes	or No
28.	Date of first fraction		
29.	Date of last fraction		_
30.	Elapsed time (days) from first fraction to last	fraction:	
31.	Institution Patient treated at:		
32.	Mode (Calypso=1, ExacTrac=2)		_

Age at time of enrollment Month and Year of birth Race Zip code Date of Prostate Biopsy Combined Gleason Score Primary Gleason Pattern Secondary Gleason Pattern Number of cores (biopsy) Number of positive cores (biopsy) Lobes (Right, Left or Bilateral) Duke Pathology Review (Y or N) Hx of Previous Biopsy (Y or N) PSA Date PSA level T stage Zubrod Baseline AUA Score Baseline AUA Bother score Baseline HEF Baseline

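### No CTCAE GU/GI grade is scheduled before treatment and section 7.1 has no rule for symptoms already present, so the Grade 2+ late toxicity and GU/GI incidence results cannot separate old symptoms from new ones

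*Combined protocol and SAP*

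**What the plan says.** **When toxicity is graded.** The assessment table in section 6.6 has a row "Toxicity Assessment" with marks during radiotherapy and at 1, 3, 6, 12, 18, 24 and 36 months. The Baseline and SBRT Planning cells are empty. Section 6.5 places the "assessment of specific GU and GI toxicity" at the follow-up visits. Section 6.8 adds: "Adverse events will be recorded at each study visit".

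**What is known at baseline.** Section 4.1 lists "International Prostate Symptom Score (IPSS)/American Urological Association Symptom Score, International Index of Erectile Function (IIEF-5) and EPIC-26 QOL". The 6.6 table adds a medical history. Appendix 3 carries "Baseline AUA Score Baseline AUA Bother score" and a baseline IIEF entry, but no CTCAE GU or GI grade.

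**Who may enter.** Section 3.3.4 excludes "Significant urinary obstruction (i.e. AUA Symptom score > 18", so a man with a score of 18 or less is eligible. For bowel disease, section 3.3.11 excludes Crohn's disease and ulcerative colitis.

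**What is counted.** Section 3.1 makes late toxicity of Grade 2 or worse at two years the primary endpoint. Section 2.1 states the objective as the incidence of acute and late GU and GI toxicity. Section 7.1 scores events by CTCAE v4.0 and calls them acute up to 90 days after radiotherapy ends and late after that. It sets no condition that an event be new, worse than before treatment, or related to treatment.

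**The concern.** A man can enter with urinary frequency or urgency, and section 5.8 lists both among the possible radiation side effects. If the symptom is unchanged at a visit more than 90 days after treatment, the grader has no earlier CTCAE grade to compare it with and no written rule on whether to count it. One grader may score what is present; another may discount it from memory or from the history. Section 6.5 allows follow-up with referring providers, so different people may make that judgement.

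Counting old symptoms inflates the toxicity rate. Informal discounting can also remove genuine worsening. In a randomised trial the background would appear in both arms. This trial has one arm, so the background remains in the estimate, and the estimate is the main product of the study.

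**Working it through.** **1. Does another part of the plan supply the missing grade or rule?**

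| Place | What it offers | Does it close the gap? |
|---|---|---|
| 6.6 table | Toxicity grading from radiotherapy onward | No baseline grade |
| 6.5 | GU/GI assessment at follow-up | After treatment only |
| 6.8 | Events recorded at study visits | Could be read to include the presentation visit in 6.1, but neither the table nor Appendix 3 provides for it |
| 4.1, 6.6, Appendix 3 | AUASS, IIEF, EPIC-26, history | Other scales; no mapping to CTCAE |
| 5.9 | Relatedness categories | Tied to reporting requirements, not to endpoint counting |
| 7.1 | Unadjusted and adjusted odds ratios | No covariates named; stated in the acute-event paragraph |

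None gives both a baseline CTCAE grade and a rule for using it.

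**2. The plan's own power figures (7.1), n = 60, grade 3 or higher rectal toxicity.**

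- True rate 1.5%: P(X ≤ 1) = 0.985^60 + 60 × 0.015 × 0.985^59 = 0.4038 + 0.3690 = 0.773. The plan says 77%. The upper limit of the two-sided 90% Wilson interval for 1/60 is 7.13%; the plan says 7.1%.
- True rate 2.5%: P(X ≤ 2) = 0.8105. The plan says 81%. The Wilson limit for 2/60 is 9.58%; the plan says 9.6%.

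The figures reproduce. They concern rectal events, so a pre-existing urinary symptom does not enter them.

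**3. Illustration for Grade 2+ toxicity.** Let t be the true rate of new Grade 2+ toxicity and b the share of men with a baseline grade 2 symptom that persists past 90 days and is counted. If the two are independent, the observed rate is r = t + (1 − t) × b.

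- t = 20% is the grade 2 GU rate (8/40, with no grade 3–5) in the 40-patient five-fraction series in section 1.3. That series called toxicity late from 30 days, whereas 7.1 uses 90 days, so it is only a reference value.
- b is not in the documents. The values 5%, 10% and 20% are assumptions.

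| b | r | Expected men of 60 (60 × r) |
|---|---|---|
| 0% | 20% | 12.0 |
| 5% | 0.20 + 0.80 × 0.05 = 24% | 14.4 |
| 10% | 0.20 + 0.80 × 0.10 = 28% | 16.8 |
| 20% | 0.20 + 0.80 × 0.20 = 36% | 21.6 |

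**4. The stopping table (7.4).** The boundaries are ≥ 3 of 15 and ≥ 4 of 30. The probability of crossing is 1 − Σ P(X₁ = a) × P(X₂ ≤ 3 − a), summed over a = 0, 1, 2, with X₁ and X₂ independent binomial(15, p). At the acceptable rate p = 5% it is 7.5%. If 1% of men carried over a counted grade 3 symptom, p = 1 − 0.95 × 0.99 = 5.95% and the probability is 11.9%. At 2%, p = 1 − 0.95 × 0.98 = 6.9% and it is 17.1%. The rule is sensitive to small inputs, but the documents give no reason to think that any such grade 3 carry-over exists.

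**The case against.** **The definition already excludes old symptoms.** Section 5.9 defines an adverse event "regardless of whether it is considered related to the medical treatment or procedure". A reader might infer from those words that pre-existing symptoms must be counted. The documents do not support that. The same sentence requires the event to be temporally associated with treatment, which an unchanged older symptom arguably is not. It also sits in the reporting section, and relatedness, including an unrelated category, is to be recorded. The objective and the design section speak of toxicity. This objection stands: the plan is silent on the point and does not direct that old symptoms be counted. But silence leaves each grader to decide, without a baseline grade.

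**Baseline status is known in another form.** EPIC-26 asks about leakage, burning, bleeding, frequency, bowel urgency and bloody stools. Together with AUASS and the history it gives a fair picture. This stands in part: it makes retrospective grading possible, but no rule says how to do it or that it should be done.

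**A mark may have been lost.** Footnote 3 of the 6.6 table has no visible anchor in the text reviewed, so a lost mark cannot be fully excluded. Section 6.5 and Appendix 3 independently point to the same gap.

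**Overstating toxicity is conservative.** That is true for counted old symptoms. It does not hold for inconsistent discounting.

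**Conclusion.** The point holds for the Grade 2+ late toxicity endpoint in 3.1 and the incidence objective in 2.1, mainly on the GU side, because the AUA entry limit concerns urinary symptoms only. Followed as written, the trial will lack a like-for-like baseline against which to separate old symptoms from new ones. That is more than missing detail, because the grade cannot be recovered exactly later.

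The size cannot be fixed from the documents. The 24% to 36% range rests on an assumed 5% to 20% carry-over, on independence from new toxicity, and on every such symptom persisting and being counted. It shows what the gap could do and is not an estimate.

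Two stronger readings are tempting:

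- A reader might infer that the whole primary endpoint is compromised. The power statement in 7.1 concerns grade 3 or higher rectal toxicity, which urinary symptoms do not touch.
- A reader might infer that the stopping rule would be triggered falsely. No pre-existing grade 3 prevalence is given or implied. Crossing a boundary leads to temporary closure and review of the source records, where an old symptom could be recognised. No material effect is shown.

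**What to change.** 1. In the 6.6 table, mark Baseline in the Toxicity Assessment row: CTCAE v4.0 GU and GI terms, graded before fraction 1. Add a matching field to Appendix 3.
2. In 7.1, define treatment-emergent toxicity for each CTCAE term as a term not present at baseline, or a grade above that term's baseline grade. The comparison must be by term. A comparison of the worst grade within an organ system would miss new grade 2 hematuria in a man who entered with grade 2 frequency.
3. Use this definition for the Grade 2+ GU and GI incidence, and report the crude absolute-grade rate beside it so that nothing is hidden.

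The cost is one extra grading at a visit that already takes place and a minor amendment. For men already treated, the baseline grade would have to be back-filled from history, AUASS and EPIC-26. That is less exact, and those grades should be flagged as retrospective.
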